**2e. Profile of Mood States:**

The POMS is a checklist of 65 adjectives describing mood states (Lorr et al, 1971. The subject rates the presence of each mood state in the past week on a 5-point scale from "not at all" to "extremely." The POMS is scored for 6 scales (fatigue, vigor, depression-dejection, anger-hostility, tension-anxiety, and confusion-bewilderment). All scales but the vigor scale are scored such that higher scores reflect greater mood disturbance; for the vigor scale, higher scores reflect less mood disturbance. The test is scored for each scale as well as for a total mood disturbance score derived from summing all scales (with reversal of the negatively scored items on the vigor scale). The POMS has been shown to be sensitive to AEDs in prior studies (Meador et al, 2014a, 2014b).

The Total score for POMS is the primary measure for Z score for this measure.

**2f. Columbia-Suicide Severity Rating Scale (C-SSRS)**

Suicidality will be assessed by trained study personnel using the C-SSRS (Columbia University Medical Center, 2008). This scale will be used for screening as well as to assess suicidal ideation and behavior that may occur during the study.

This is a safety measure and is not used in the primary analysis.

## **VIII. STUDY MEDICATIONS**

**A. Description**

ESL 400mg, Carbamazepine (immediate release) 200mg, and placebos will be provided by Sunovion or their designee. All AED doses and placebos will be overencapsulated in matched opaque capsules.

**B. Packaging and Labeling**

Medications will be provided by Sunovion in capsule bulk containers. Each will be labeled with the appropriate contents, ESL 400mg capsules, Carbamazepine 200mg (immediate release) capsules and matching placebo. All drugs will be identical capsules. Sunovion will supply plastic containers with tid daily dose sections for each patient. The clinical research pharmacy will be responsible for dispensing and labeling study drug for the study subjects.

**C. Shipment and storage**

Sunovion or their designee will ship all drug supplies to the site. A shipping invoice will be contained with each shipment and should be kept and matched against received drug. All investigational drug will be stored and locked in the Clinical Research Pharmacy. All unused drug supplies remaining at end of study will be destroyed by the site pharmacy personnel and written notification of the destruction will be sent to Sunovion. Study drug should be stored in

the drums it is shipped in, in a cool dry area until drug is dispensed to the study subjects.

**D. Maintenance of medication dispensing records**

Each clinical pharmacy site will provide medication dispensing instructions and forms for recording dispensing of study medications to the pharmacy study personnel. These records should be kept current during the study and be available for inspection. When medication is dispensed, the number of capsules of active and placebo are to be listed on the appropriate dispensing log. Returned capsules at each visit will also be recorded.

**E. Return of unused medication**

At each visit, subjects must return the medication packets and all unused study medication to the investigator. The accountability for returning of medication is the responsibility of the investigator. Unused study drug returned by subjects will be destroyed in accordance with remainder study drug.

**F. Concomitant medication and therapy**

Subjects will be instructed to limit alcohol consumption to no more than ½ ounce of absolute alcohol equivalents per day (approximately one 12 oz. beer, or 1 mixed drink) and no more than 3 ounces per week. Subjects will be instructed not to consume alcohol, caffeine, or take any over-the-counter medications for at least 72 hours prior to cognitive and behavioral testing. All concomitant medications will be recorded on the case report forms. Any concomitant medications and other agents, which are known to affect Carbamazepine or Eslicarbazepine or have significant effects on cognition may not be taken during this trial. A partial list of examples include: anticholinergics, anticoagulants, antidepressants, antiepileptics, antipsychotics, anxiolytics, central nervous system depressants, corticosteroids, doxycycline, erythromycin, H2 antagonists, lithium, methylphenidate, narcotics, quinidine, reserpine, theophylline, centrally active antihistamines, and grapefruit juice. Informed consent will emphasize that subjects should not consume grapefruit or its juice during the study.

**IX. CLINICAL AND LABORATORY MEASUREMENTS**

**A. Clinical Measurements (Study weeks -1, 0, 6, 10, 16, 20)**

Neuropsychological testing will be completed at baseline (visits 1 & 2), at the completion of each AED treatment period (weeks 6 & 16) and at the completion of each washout period (weeks 10 & 20). The neuropsychological test results from the first baseline testing (i.e., visit 1 at -2 weeks) will not be included in the analyses. All subjects will have at least 7 hours of sleep on the evening before the day of cognitive testing. (Note. If the subject does not get the required hours of sleep or takes non-approved medication, caffeine, etc., cognitive and behavioral testing will be rescheduled).

For detailed information regarding all of the cognitive tests refer to Section VII.

B. Clinical Safety Measurements

1. Physical Examinations (Study weeks -1, 0, 6, 10, 16, & 20)

A complete physical and neurological examination will be performed during pre-study screening (visit 1; week -1) and at the completion of the study (visit 6; week 20) or study discontinuation. Brief physical examinations will be performed on visits 2, 3, 4, & 5 (weeks 0, 6, 10, & 16).

A complete physical examination will consist of determinations of sitting blood pressure, weight, heart rate, assessment of physical condition (general appearance, skin and skin structure, HEENT, abdomen, cardiovascular, respiratory, musculoskeletal, genitourinary and central nervous systems). Brief physical examinations will consist of determinations of sitting blood pressure, weight, heart rate, and an assessment of physical condition, as required to determine change from the previous visit, and an assessment of adverse effects focused on skin and neurological systems.

2. Laboratory assessments (Weeks -1, 6, 10, 14, 18)

A. Blood and Urine Samples

Blood work assessments will be obtained at visits 1, 6, 16, & 20.

The hematology parameters to be determined are: RBC count, hemoglobin, hematocrit, WBC count, platelet count, cell morphology and complete WBC differential count (neutrophils, bands, lymphocytes, monocytes, eosinophils and basophils).

The chemistry parameters to be determined are: SGOT, SGPT, alkaline phosphatase, albumin, total protein, total bilirubin, sodium, potassium, chloride, calcium, phosphorous, creatinine, blood urea nitrogen, uric acid and glucose. The total chem panel will be obtained at visits 1 & 6; just SGOT & SGPT will be obtained at visits 3 & 5.

Urine Pregnancy tests will be performed on women of childbearing potential at Weeks -1, 10 & 20 (visits 1, 4 & 6).

In subjects of Asian descent, blood will be obtained to test for the HLA B\*1502 allele. If present, subjects will not receive drug or continue in the study. Subjects lost for this reason will be replaced by new enrollees.

Anticonvulsant blood levels will be collected at Weeks 6 and 16 (i.e., visits 3 & 5). Carbamazepine levels are to be sent to the hospital laboratory for immediate

analysis. The Eslicarbazepine and Carbamazepine levels will be sent to an outside contract lab. Results are to be reviewed and stored by the non-blinded investigator.

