## **VI. STUDY PROCEDURES**

A. Overview: time and events

The study will employ a double-blind, randomized, two-period crossover design. The study consists of 6 visits over a 21 week time period. Subjects will be screened and tested at baseline, and then randomly assigned to receive each AED for 6 weeks, which includes a titration period and a one-month maintenance period. Each AED treatment period will be followed by a 3-day taper and a washout period for the remainder of 4 weeks. (See Appendix A for a complete study timetable).

B. Blinding and Controls

Subjects and study personnel will be blinded to drug randomization since all study drugs will be over-encapsulated in identical capsules.

C. Dosage Regimen

During each AED phase, subjects will be titrated onto ESL (800mg/day) or

Carbamazepine (400mg bid) and tapered off at end of 4-week maintenance according to the following schedule during each treatment arm:

Week	ESL	Carbamazepine
1	400 mg qAM + placebo	200 mg bid
2	400 mg qAM + placebo	200 mg qAM & 400mg qHS
3	800 mg qAM + placebo	400 mg bid
4	800 mg qAM + placebo	400 mg bid
5	800 mg qAM + placebo	400 mg bid
6	800 mg qAM + placebo	400 mg bid
3-day taper	400 mg qAM + placebo	200 mg bid
Stop		

The investigative team will monitor each subject's progress and safety during AED treatment periods with the goal of obtaining and maintaining ESL and Carbamazepine at dosage of 800mg/day. Subjects will remain on each AED for a total of 6 weeks (4 weeks maintenance), and then will be tapered off over 3 days followed by washout period for the remainder of 4 weeks. Total time on each drug will be 6 weeks plus 3 days. ESL will be dosed qAM and Carbamazepine will be dosed BID. The plasma  $T_{max}$  for plasma eslicarbazepine and carbamazepine will therefore approximately match the time of testing. Subjects will be tapered off AEDs over the first 3 days of each 4-week washout period according to the following schedules:

AED Dose DURING TRIAL

ESL = 800

Carbamazepine = 800

AED TAPER

400mg daily X3 days then stop

200mg bid X3 days then stop

An appropriate number of placebo capsules will be added to all AED dosages so that subjects will always take the same number of capsules for each dose given BID during AED treatment periods. Dosage times will be 8am and 8pm.

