**Study weeks 6 - 10**

The subject will be tapered off drug over the first 3 days and then remain off drug for the next 25 days.

**Visit 4**      (Study week 10)

This visit ends the washout period and begins the baseline for Drug Period 2. At this visit, vital signs and a brief physical examination will be obtained. Subjects will undergo cognitive and behavioral testing and then the alternate drug treatment will be dispensed. Titration will be similar to the first titrations beginning at Visit 2. In addition, a pregnancy test will be obtained in women of child bearing potential.

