Summary statistics will be calculated by treatment for each evaluation of antiepileptic blood levels (ABLs). Additional analyses of data will be performed which take the ABLs into account. Linear correlations of plasma concentrations and the overall composite and individual score variables will be plotted with a fitted regression line superimposed for each drug condition.

The incidences of all adverse events reported during the trial will be tabulated by treatment and study period. The other safety variables, which include changes in hematology, clinical chemistry, and urinalysis parameters, and vital signs will be analyzed descriptively. The actual measurement and its change from Baseline will be presented by visit and period of collection. In addition, shift tables may be used to evaluate the number and percentage of subjects having a different post-Baseline status when compared with their Baseline status.

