### APPENDIX A - STUDY TIMETABLE

PROCEDURE	SCREENING	FIRST		TAPER/ WASHOUT	SECOND		TAPER/ WASHOUT	FINAL VISIT
		DRUG PERIOD			DRUG PERIOD			
Week	-1	0	1 to 6*	7 to 10	11 to 16*	17 to 20	20	
Visit	1	2	3	4	5		6	
Informed consents	X							
Complete Physical & Neurol. Exam	X							X a
Brief Physical Exam			X		X		X	
CBC, Chem	X		X b			X b		X a
Pregnancy Test	X c			X c				X a,c
HLA B*1250	X d							
ABLs			X			X		
Cognitive & Behavioral Testing	X e	X	X	X		X		X
Phone call		X f X f			X f X f			
Study Drug Dispensed		X		X				

\* Calls are made at weeks 2, 4, 12 and 14 to check on AEs and to encourage compliance.

a Done if patient discontinues early, or at last study visit

b Just CBC, SGOT & SGPT on these dates.

c Done only in women of child bearing potential

d HLA B\*1250 testing in subjects of Asian descent

e Screening tests include Peabody IQ at first visit only, then remainder of neuropsychological battery (which is repeated each testing session)

f Research coordinator will call subjects on weeks 2, 4, 12 & 14 to check on side effects.

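### Thirteen of the 15 listed chemistry parameters have no scheduled on-drug value in completers, and blood already drawn at Visits 3 and 5 could supply it (minor, descriptive safety data only)

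*Combined protocol and SAP*

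**What the plan says.** Section IX.B.2 of the combined protocol and SAP names 15 chemistry parameters and then divides them by visit: "The total chem panel will be obtained at visits 1 & 6", while "just SGOT & SGPT will be obtained at visits 3 & 5". Footnote b of the Appendix A timetable attaches to the two drug-period laboratory entries and says the same: "Just CBC, SGOT & SGPT on these dates".

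Other texts bear on the point:

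- **Visit 3 and Visit 5 descriptions (Section VI.E).** Both call for blood levels, CBC and chemistries, without saying which chemistries.
- **Visit 4 description (Section VI.E).** Vital signs, a brief examination, cognitive testing and, where relevant, a pregnancy test are done, "and then the alternate drug treatment will be dispensed". No chemistry is listed there or in the timetable.
- **Section IX.E.5 and Appendix A, footnote a.** Subjects who stop early after receiving drug have a laboratory evaluation that includes chemistry, to be done promptly. No interval from the last dose is set.
- **Section X.B.** Laboratory variables and vital signs "will be analyzed descriptively", as values and changes from Baseline, by visit and collection period. Adverse events, by contrast, are tabulated by treatment.

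**The concern.** Visits 3 and 5 are the only scheduled clinic visits at which a subject is at the end of maintenance on a study drug. If only SGOT and SGPT are measured there, the remaining 13 parameters are measured before either drug and again after both have been washed out. Their change from Baseline in a completer cannot describe a change during treatment and cannot be attributed to one drug, because by Visit 6 every completer has taken both. The second drug also starts at Visit 4 with no scheduled repeat of these 13 after the first.

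What is at stake is the usefulness of part of the safety description: parameters that the plan itself lists are not scheduled at the times when they would say something about the drugs.

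**Working it through.** The plan states no figure on this point, so the check is a count against the schedule.

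**1. Parameters.** Section IX.B.2 lists SGOT, SGPT, alkaline phosphatase, albumin, total protein, total bilirubin, sodium, potassium, chloride, calcium, phosphorous, creatinine, blood urea nitrogen, uric acid and glucose: 15. Removing SGOT and SGPT leaves 15 − 2 = 13.

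**2. Scheduled chemistry in a completer, under Section IX.B.2 and footnote b.**

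| Visit | Week | Drug status | Chemistry |
|---|---|---|---|
| 1 | −1 | before any drug | all 15 |
| 2 | 0 | before any drug | none |
| 3 | 6 | on first drug | SGOT, SGPT |
| 4 | 10 | off drug 25 days | none |
| 5 | 16 | on second drug | SGOT, SGPT |
| 6 | 20 | off drug 25 days | all 15 |

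Each of the 13 therefore has 0 scheduled values under ESL and 0 under CBZ. SGOT and SGPT have one per drug. With no chemistry at Visit 2, Visit 1 is the only pre-drug value that can serve as Baseline.

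**3. Length of the gap.** Section VI.C: "Total time on each drug will be 6 weeks plus 3 days", so 6 × 7 + 3 = 45 days per drug and 2 × 45 = 90 days on drug. Week −1 to week 20 is 21 weeks, or 21 × 7 = 147 days. Drug is taken on 90/147 = 61% of the days between the two full panels.

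**4. Early discontinuers.** Section X.A expects 30% to 40% dropout. Of 50 enrolled that is 0.30 × 50 = 15 to 0.40 × 50 = 20 subjects. Those among them who had received drug would have a chemistry evaluation under Section IX.E.5, which may fall on drug, near drug or after it.

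**5. What full panels at Visits 3 and 5 would give.** In 30 completers, each parameter would have 30 on-drug values per drug.

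- If none of 30 is abnormal, the one-sided 95% upper bound on the abnormality rate is 1 − 0.05^(1/30) = 9.5%.
- The chance of at least one abnormal value per drug is 1 − (1 − p)^30, which is 45% for p = 2%, 79% for p = 5% and 96% for p = 10%.

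The rates p are assumed, since the documents give none. These are binomial results for any sample of 30. They show roughly what such a sample can reveal, and do not measure mean change or a difference between the drugs.

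**6. Added assays.** 13 × 2 visits = 26 per completer; 26 × 30 = 780 for 30 completers; 26 × 50 = 1,300 if all 50 enrolled reached both visits.

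**The case against.** The strongest reply is that the reduced on-drug panel is a deliberate choice, stated in two places that agree, in a study whose question is cognitive and behavioral. Section X.B can be carried out as written, and it does not promise chemistry by treatment. All of that stands, and it is why this is a suggestion for improvement.

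A reader might infer that the trial will have no on-drug chemistry at all for these parameters. The documents do not support that. Section IX.E.5 provides chemistry for subjects who stop early, possibly a sizeable group, and unscheduled tests are possible. The point covers scheduled values in completers only.

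A reader might also take Section IX.B.2 as settled. The protocol states no order of precedence, and the Visit 3 and Visit 5 descriptions could be read as ordering the full panel. Section IX.B.2 and footnote b are more specific and agree with each other, so they are the more natural reading, but that is an inference. The week and visit labels in Section IX.B.2 are also inconsistent. Its heading includes week 10, which is Visit 4, perhaps because of the pregnancy test. The sentence that assigns parameters to visits still gives the full panel only to Visits 1 and 6.

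Finally, nothing in the documents says that any of the 13 is expected to change on either drug, so clinical importance is not shown. CBC, SGOT and SGPT, vital signs, examination, drug levels and adverse-event calls already provide cover during treatment.

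**Conclusion.** The point holds as a minor, inexpensive improvement to descriptive safety data. Under Section IX.B.2 and footnote b, 13 of 15 listed parameters have no scheduled on-drug value in completers, and their planned change from Baseline compares two drug-free visits 147 days apart. The count is exact. It rests on those two texts governing over the looser visit descriptions; if the full panel was intended at Visits 3 and 5, the values would exist and the defect would be a contradiction between sections, cured by the same amendment.

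It would go too far to conclude that the safety analysis fails, that subjects are shown to be at risk, or that the comparison of the drugs is weakened. The cognitive endpoint, CBC, SGOT and SGPT, vital signs and adverse-event data are unaffected.

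**What to change.** 1. Run the full listed chemistry panel at Visits 3 and 5, on the blood already drawn there for CBC, SGOT and SGPT, and drug levels.
2. Amend Section IX.B.2 and footnote b of Appendix A so that they agree with the Visit 3 and Visit 5 descriptions in Section VI.E.
3. In Section X.B, summarise the on-drug values by treatment as well as by visit and period. In a crossover, each of Visits 3 and 5 mixes subjects on the two drugs, so a table by visit alone describes neither.
4. State who reviews the added results. The non-blinded investigator is a natural choice, but the present instruction, "Results are to be reviewed and stored by the non-blinded investigator", covers only drug levels and would need extending.

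As housekeeping, correct the week and visit labels in Section IX.B.2, and either schedule urinalysis or remove it from Section X.B, since no visit explicitly schedules it for completers.

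The cost is 13 more assay results at each of the two visits (780 for 30 completers, with a ceiling of 1,300) and the time to review them. No visit or venipuncture is added.

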### C. Adverse Event Procedures

An ADVERSE EVENT (AE) is a noxious and unintended event observed in, or reported by, a subject who is participating in (or has participated in) a clinical study and/or has received study medication. The AE may be related temporarily either to immediate or long-term use of the drug; the AE may not necessarily be caused by the drug. Overdose is regarded as an adverse event. Any event meeting these criteria is to be considered an adverse event, regardless of whether or not it is considered drug related.

All adverse events should be reported on the appropriate Case Report Form; details should include the type of event, date of onset, duration, intensity, causality relationship to the study drug(s), and outcome. Wherever possible, a diagnosis rather than symptom(s) should be reported.

“Serious” means an adverse experience that is fatal or life-threatening, is permanently disabling, requires or prolongs inpatient hospitalization, or is a congenital anomaly, cancer or overdose.

If any medically serious adverse event occurs (SAE), the study medication may be discontinued and the patient treated at the discretion of the physician investigator.

ANY MEDICALLY SERIOUS ADVERSE EVENT REQUIRES IMMEDIATE  
NOTIFICATION OF THE FDA BY THE INVESTIGATOR.

Any serious adverse event that occurs up to two weeks following study participation must also be reported.

#### Specific procedures for Double-Blind Studies

Site personnel not involved in direct care of study subjects will generate a randomization code. In an acute medical emergency, the randomization code may be broken if this is considered essential for subject management. For this purpose the sealed randomization code will be provided to the investigator by the site pharmacy. If the code is broken, a record of the date, time and reason must be put into writing and sent to Sunovion. This letter will become part of the permanent study record.

All adverse events should be recorded on the appropriate Case Report Forms (CRF's) including date of onset and cessation, intensity and relationship to study drug. The action taken and clinical outcome of the adverse event will also be recorded.

The investigator will report all serious AE's to the FDA and to Sunovion without delay.

#### D. Medication Compliance Assessment

Compliance is to be judged by questioning the patient at the clinic visit and by the non-blinded observer's inspection of medication returned and recording missed doses on the appropriate CRF. Repeated noncompliance, or the missing of all scheduled doses of medication for three (3) consecutive days (72-hour period) would be cause for removing the subject from the study. Subjects should take all doses for 3 days before visits when cognitive function testing occurs.

#### E. Subject Discontinuation Criteria

1. Although they may withdraw without prejudice at any time, every effort should be made to have subjects complete the study within the bounds of safety and provisions of informed consent.
2. The investigator may discontinue the participation of any subject in this study if:
  - a. Any clinically significant adverse experiences are observed.
  - b. The subject is grossly noncompliant.
  - c. The subject's health would be jeopardized by continued participation.
  - d. Consent is withdrawn. Otherwise, subjects will be encouraged to complete the study, although they may withdraw at any time without prejudice.
3. If subject cannot tolerate the 800 mg/day dose of ESL or Carbamazepine, the dose may be reduced to 400 mg/day if the subject and physician deem appropriate. An attempt to increase the dose a week later can be made. If they choose not to reduce the dose or if the subject cannot tolerate at least 400 mg/day, then the subject will be discontinued.
4. Subject replacement.

Subjects who are dropped from the study prior to completion of all cognitive testing will not be replaced.

